## **Study Specific Experimental Procedures**

1. Fluciclovine PET-CT imaging: PET-CT images will be acquired on a state-of-the-art scanner. All studies will use measured attenuation correction (routinely acquired through the initial CT portion of the scan). All subjects will fast for 4 hours to normalize their neutral amino acid levels. Within 1 hour prior to scanning, the patient (if able) will drink up to 450 ml of standard oral contrast. IV contrast will not be used. After completion of the CT scan, approximately 10 mCi anti-[18F]FACBC will be injected into an antecubital vein as a bolus and flushed with normal saline. Scanning will commence immediately as technically possible starting with the pelvis at 2.5 min/bed for 2 bed positions (from just below ischium to approximately bifurcation); this sequence will be designated. early 0-5 minutes. At 5 minutes, 7 consecutive 2.5 minute/frame acquisitions will be obtained from the pelvis (below ischium) to approximately the skull base. At 22.5 minutes, a delayed 2 bed similar pelvis will then be acquired from the 22.5 to 27.5 mins. Thus, we will have early (effectively 10 min multi-time point imaging of the pelvis) and 10-22.5 min imaging from pelvis inlet to skull base. This acquisition is similar to a successful protocol with FACBC for primary prostate cancer staging employed at Aleris Medical Center in Oslo, Norway (personal communication, [name]), but also allows us to cover the entire pelvis to the bifurcation and also obtain an exploratory final 5 minutes delayed acquisition of the pelvis. The whole body acquisition itself is similar to that employed clinically. Scanning will preferably be undertaken arms above the head if possible for the patient.

#### Image Analysis of FACBC PET-CT:

- 1) Images will be reconstructed with iterative technique and interpreted on a MimVista or similar workstation.
- 2) Visual inspection of the PET-CT images by a board certified nuclear medicine imager, blinded to other imaging, will then occur and results recorded on a case report form. (It is possible that as part of clinical duties, the research reader may have interpreted one of the patient's earlier clinical exams. This type of situation is impossible to avoid, but it is highly unlikely that recall of an individual exam would be possible with our institutional workflow. Therefore, this situation is still considered as *blinded* for the purpose of this study.)
- 3) Uptake will be defined according to the following criteria in relation to background structures: mild (above blood pool but less than marrow), moderate (above or equal to marrow but less than liver), and intense (equal to or above liver). Visual analysis will aided by quantitative criteria of SUVmax lesion/SUVmean background. Maximum and mean SUV of each focus of abnormal uptake and background will be recorded. SUV (mean, maximum, peak, total lesion activity) will also be documented for the prostate primary lesion(s) as a whole gland ROI at all time points to calculate uptake and retention indices. For extra-prostatic sites such as lymph nodes and bone, abnormal moderate or intense focal uptake which are present on 5-27.5 minute images will be considered prospectively positive (allowing for partial volume effect). Analysis will be supplemented by data from early and delayed time point acquisitions of the pelvis and is most useful to increase sensitivity for small lesions subject to partial volume effect on PET and also increase specificity. These criteria were successfully used in our studies of FACBC in recurrent disease [4, 50]. The multi-time point data of the pelvis will also be used for future analysis of uptake in comparison to the reference histologic standard likely on a sextant basis. If possible. we will use a segmentation algorithm under development to assist with this analysis.
- 4) A final review of the images by the nuclear medicine imager and the urologist will occur to ensure that nodal regions are understood in a similar manner and determine if areas of uptake will be in the field of operation. For example that internal iliac means the same to the imager and the surgeon.

#### Histologic Assessment:

The histologic examination of the nodal tissue will be done using standard clinical protocols. The surgical specimens will be submitted with each of the nodal groups separately identified with appropriate labels. This will ensure that the pathology reports will be evaluable for the presence of positive nodes in each of the nodal groups, and that it will be feasible to correlate the pathology data with the imaging data.

- The FACBC readings for nodal groups in each patient will be compared against the histologic results. To ensure proper correlation of both FACBC and histologic results, FACBC nodal reads will be labeled according to the packets listed in #2 above. This will also guide nodal dissection and labelling of nodal tissues for pathologic analysis.
- 2) The readings for skeletal disease will also be compared to biopsy and definitive correlative imaging as appropriate. Criteria for skeletal metastasis are considered more well established than for lymph nodes and therefore biopsy may not be needed in the case of skeletal metastasis if two separate conventional imaging modalities such as MR, CT, and/or bone scan are concordant in probability for skeletal malignancy [51].
- 3) At a later time point the prostate sextant histologic data will be compared to best matching imaging sextant based on automatic or manual segmentation and correlation of uptake indices made with tumor, Gleason grade, inflammation, and BPH as well as other potential imaging and histologic analysis.

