#### 9. Statistical Analysis and Power Calculation

In calculating statistical power we have taken realistic suppositions. The prevalence estimate of occult metastatic disease, FACBC sensitivity and specificity is extrapolated from reported large series and nomograms, as well as data culled from our previous trials and clinical experience [4, 5, 48, 52, 53]. The primary goal of the study is to estimate the rate of positive FACBC studies in this population for occult extraprostatic metastasis. We therefore assumed a 50% prevalence of occult metastasis (metastases not definitively evident on routine clinical imaging), 95% specificity, and a conservative sensitivity of 40%. They translate to 22.5% FACBC scans to be positive (note that FN included) and 89% PPV. We plan to enroll 88 patients to have 0.8 power for detecting the rate of positive FACBC to be at least 10%. The number of patients with positive FACBC is expected to be 20, and the number is between 12 and 28 with 0.95 probability. In addition to the point estimate, 95% CI will be calculated for the rate of positive FACBC and a statistical test will be conducted against the null hypothesis of a rate of 10%.

As part of the secondary analysis, we will cross-tabulate the FACBC classification versus extraprostatic disease status as detected by extended pelvic nodal dissection as outlined above. Note that the latter is not regarded as a gold standard for extraprostatic disease detection since it may still results in substantial false negatives. Nevertheless, the percent of positive FACBC among patients with extraprostatic disease detected by extended pelvic nodal dissection provides a reasonable estimate of the sensitivity for FACBC. We will calculate the corresponding exact 95% confidence interval. In addition, we will evaluate the extent to which the FACBC and extended pelvic nodal dissection agree with each other using kappa statistic. This analysis of concordance will help guide design of analyses of tissue-imaging concordance in the subsequent, Phase III Validation Trial (ECOG-ACRIN), to comprehensively evaluate the diagnostic characteristics of FACBC.

For Aim 2, we will assess associations between FACBC uptake parameters in the prostate and rate of extraprostatic disease detection using standard associative statistical tools including logistic regression and ANOVA as applicable.

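### Section 9 estimates sensitivity per patient without requiring the FACBC-positive site to match the histology-positive packet, so it can overstate sensitivity for nodal disease; a location-matched estimate should be reported beside it

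*Combined protocol and SAP*

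**What the plan says.** **How the data are recorded.** Section 4 (Standard of Care Procedures, item 2) names four bilateral node groups and one central group, so nine standard packets, plus optional sites. Each is removed and labelled separately. Under Histologic Assessment, the FACBC nodal reads carry the same packet labels, and "The FACBC readings for nodal groups in each patient will be compared against the histologic results". Imager and surgeon also confer before surgery so that regions mean the same thing to both. Skeletal readings are compared separately with biopsy or definitive imaging. For the prostate itself, at a later time, "the prostate sextant histologic data will be compared to best matching imaging sextant".

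**What counts as positive.** Section 4 (Image Analysis of FACBC PET-CT, item 3) applies one uptake rule to extraprostatic sites in general, with lymph nodes and bone as examples.

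**What is analysed.** For the secondary analysis, Section 9 states that "we will cross-tabulate the FACBC classification versus extraprostatic disease status as detected by extended pelvic nodal dissection as outlined above". It takes the percentage of FACBC-positive patients among those with disease on dissection as a reasonable estimate of sensitivity, with an exact 95% interval, and adds a kappa for agreement. It cautions that dissection is not a gold standard. It gives no rule linking the site of uptake to the involved packet, and no packet-level or sextant-level estimate or interval.

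**The concern.** The numerator and denominator of the sensitivity estimate cover different anatomy. The denominator is men with cancer in a dissected node. The numerator is any of those men with qualifying uptake anywhere outside the prostate. A man with cancer in an obturator packet that FACBC missed, and uptake only in bone, enters the table as a detected case and as an agreement in the kappa.

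Location matters to the stated purpose. Section 4 says that preoperative findings may inform targeted nodal dissection, and Section 9 says that the concordance analysis will help design the tissue-imaging concordance analyses of the Phase III trial. For those uses, the reader needs to know how often FACBC found the disease where it was. The packet labels would answer that, but Section 9 does not use them. If the matching rule is chosen after the results are seen, two analysts could report different sensitivities from the same data.

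**Working it through.** **1. The plan's own figures.** Inputs from Section 9: prevalence 50%, specificity 95%, sensitivity 40%, null rate 10%, power 0.8. The significance level is not stated; two-sided 0.05 is assumed from the 95% interval.

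- Positive rate: 0.5 × 0.40 + 0.5 × 0.05 = 0.225. PPV: 0.20 / 0.225 = 0.889. These agree with "They translate to 22.5% FACBC scans to be positive (note that FN included) and 89% PPV".
- Sample size: (1.96 + 0.84)² × 0.225 × 0.775 / (0.225 − 0.10)² = 87.6, so 88.
- Expected positives: 88 × 0.225 = 19.8, about 20. The binomial 2.5% and 97.5% quantiles are 12 and 28, as stated.

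All of these are patient-level, and none depends on location matching.

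**2. Matched versus unmatched sensitivity.** Let s be the location-matched sensitivity and f the probability that a node-positive man missed at his involved packets is FACBC-positive only elsewhere. The Section 9 estimate then targets

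S = s + (1 − s) × f, so s = (S − f) / (1 − f).

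Since f cannot be negative, S is never below s. The documents do not give f. The 5% value borrows 1 minus the stated specificity; the others show the range.

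| f (assumed) | s if S = 40% | S if s = 40% |
|---|---|---|
| 0% | 40.0% | 40.0% |
| 2% | 38.8% | 41.2% |
| 5% | 36.8% | 43.0% |
| 10% | 33.3% | 46.0% |
| 20% | 25.0% | 52.0% |

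At f = 5%: (0.40 − 0.05) / 0.95 = 0.368, and 0.40 + 0.60 × 0.05 = 0.43.

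**3. Size against the precision available.** If half of the 88 men (44) were node-positive on dissection, 18/44 has an exact 95% interval of 26% to 57%. With 20 node-positive men, 8/20 gives 19% to 64%. At f = 5% the gap is 44 × (0.400 − 0.368) = 1.4 men.

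**4. Packets or sextants, if they are reported with intervals.** The design effect is 1 + (m − 1) × ICC, and the interval widens by its square root. The documents give no ICC; 0.05 to 0.5 is assumed.

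| Rows pooled per man | ICC | Design effect | Width factor | Coverage of an unadjusted 95% interval |
|---|---|---|---|---|
| 9 packets | 0.05 | 1.4 | 1.18 | 90% |
| 9 packets | 0.1 | 1.8 | 1.34 | 86% |
| 9 packets | 0.3 | 3.4 | 1.84 | 71% |
| 9 packets | 0.5 | 5.0 | 2.24 | 62% |
| 6 sextants | 0.05 | 1.25 | 1.12 | 92% |
| 6 sextants | 0.5 | 3.5 | 1.87 | 70.5% |

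For packet sensitivity only the histology-positive packets count. With 2 to 3 per man (assumed) and ICC 0.1 to 0.5, the design effect is 1.1 to 2.0 and the width factor 1.05 to 1.41.

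**The case against.** Patient-level sensitivity is a legitimate estimand, because the aim is to detect extraprostatic disease in a patient. Uptake away from the involved packet may be real disease: Section 3 allows skeletal biopsy and definitive imaging as reference standards, Section 4 notes that the basins sampled can vary, and Section 7 notes that FACBC-positive nodes may be missed at dissection. A matched rule used alone would count some correctly identified patients as failures. This stands, and it is why the any-site estimate should stay.

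It can also be said that location is not lost, since Section 4 commits to the nodal-group comparison and Section 9 refers back to the design text. That stands in part. The labels and the intention are there, but the definition of sensitivity in Section 9 is complete as written and contains no matching condition.

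Three stronger readings are tempting, and the documents do not support them.

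- **A reader might infer that sensitivity is inflated.** That requires f above 0, and the documents give no such rate. The stated 40% is a patient-level planning value, not a location-matched one.
- **A reader might infer that the named methods are wrong because they assume independent observations.** The Section 9 sensitivity and association analyses have one row per man: sensitivity is over patients, uptake of the primary is recorded as a whole-gland region, and the biomarkers are per man. Both association lists are also open-ended.
- **A reader might infer that intervals will be too narrow.** No packet-level or sextant-level interval is planned, and the sextant work is deferred. Pooling all nine packets also overstates the problem for packet sensitivity, where far fewer packets per man enter.

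**Conclusion.** The point holds as a limited one. The sensitivity defined in Section 9 can equal or exceed the location-matched sensitivity for nodal disease, and the plan does not report the latter although both readings carry the labels needed. The gap is about 3 points at an assumed 5% off-site-only rate, 15 points at 20%, and none at 0%. At 5% it is small beside an interval of roughly 26% to 57%. The direction for kappa is not fixed: matching removes off-site positives from the agreements in node-positive men, but also from the false positives in node-negative men.

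The clustering point is conditional. It applies only if packet or sextant results are reported with intervals, and its size rests on assumed ICCs. The effect is confined to secondary and later analyses.

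**What to change.** In Section 9:

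1. Keep the any-site, patient-level sensitivity with its exact interval.
2. Beside it, report a location-matched sensitivity and kappa. In a node-positive man, FACBC counts as positive only if at least one FACBC-positive packet matches a histology-positive packet. In a node-negative man, any FACBC-positive dissected packet should still count as a false positive; otherwise the matched table could contain none by construction.
3. State that uptake outside the dissected packets is judged against its own reference, biopsy or definitive imaging, and tabulated separately.
4. If the nodal-group comparison is reported as packet-level sensitivity, specificity or PPV, or the sextant work is reported with intervals, use patient-clustered intervals: GEE with robust variance, or a bootstrap that resamples patients.

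The cost is a few sentences and a little programming, with no new data. The matched sensitivity may come out lower than the any-site one. The primary positivity rate, its test and N = 88 stay as they are.

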#### **Tissue and Data Management:**

1) Tissue specimen obtained from participants will be formalin fixed and paraffin embedded by the Emory Pathology Department, preserved for future intra-patient genomic comparisons between primary and metastatic disease.

2) Radiological data of participants will be stored on a secured password protected database for future retrieval and follow-up as indicated.

3) Experience from this trial will be used to plan a multicenter trial in cooperation with ECOG-ACRIN, SNMMI-CTN and Blue Earth Diagnostics (corporate developer of FACBC in the US and the EU) to potentially obtain expanded FDA approval of the modality in early detection of occult metastases before primary treatment.
4) Patients will also be followed for long term outcome measures correlating FACBC findings with PSA and clinical recurrence. Though this endpoint is beyond the scope of the current trial, patients will therefore be consented for 10 year follow-up through the medical record and via selected contact.

## 5. Participant selection

- 1) Inclusion criteria
  - a. High-risk or very-high risk prostate cancer eligible for standard of care surgery
    - i. At least clinical T3a disease, and/or Gleason >8, and/or PSA>20, as per clinical assessment and routine guidelines
  - b. Unfavorable risk intermediate prostate cancer eligible for standard of care surgery
    - i. Grade Group 2 (Gleason score 3+4) with either PSA 10-<20 or clinical stage T2b-c, OR Grade Group 3 (Gleason 4+3) with PSA < 20.
  - c. 18 or years of age or older
  - d. Undergone standard of care conventional imaging (CT and/or MR; bone scan and/or NaF PET)
- 2) Exclusion criteria
  - a. Definitive findings of systemic metastasis on conventional imaging.
- 3) Recruitment: Any attempt to recruit a large cohort of subjects is always a possible limitation. We believe with the typical numbers of patients for this clinical question seen at Emory hospitals including ESJH hospital per year (approximately 50), we will be able to achieve our target goal of 18 patients per year at a conservative 36% recruitment rate. We have an on-site cyclotron and radiopharmacy staff with a proven ability to manufacture FACBC. Thus, we have the capacity to scan these subjects. If accrual is lagging, we also have the capability to open this trial at our sister institutions, Grady Hospital and the Atlanta VA.
- 4) Dropout: We have factored in an extra 2 scans for unforeseen difficulties, but since the endpoint of the study is FACBC imaging, even if a patient does not undergo surgery, sufficient data will have been obtained for the primary analysis. Therefore patient dropout is not considered to be highly relevant in this design. We will seek IRB approval of sufficient patients to allow for screening failures, but these patients will not have undergone FACBC imaging.

## 6. Informed Consent Process

Informed consent is required prior to participation in the study. Patients will sign the written informed consent, if possible, at the time of enrollment. In instances where this is not possible, verbal informed consent will be first obtained in order to instruct the patient to fast in preparation for the PET scan. However final written informed consent will be obtained before the PET scan. Participants will also be assigned an identification number for screening purposes; data collected during the screening process will also be recorded using that number. Consent would also be obtained for RNA, DNA and other genomic analysis on urine and other indicated biofluids.

## 7. Incidental Findings

- a. All incidental findings noted by the imager will be discussed with the attending urologist who is a coinvestigator, and documented in the electronic medical record.
- b. Incidental findings (such as incidental lung nodule for example) will be disclosed to the patient who

will then formulate a follow-up plan with the attending urologist including any referrals.

- c. The urologist will educate the patient about the nature of the incidental finding, how to seek care from a clinician or specialist, obtaining health insurance to secure treatment, and/or referral to a clinical specialist, if one is required.
- d. Language to this effect is present in the consent form.

It is possible that nodes may be missed that are FACBC positive even with nodal dissection leading to an overestimation of false positivity of FACBC. If this is suspected, patients may be followed with conventional imaging as per routine to clarify the ground truth in specific situations. Also, a patient could then be enrolled in an ongoing clinical trial at Emory for PSA failure after prostatectomy (R01 CA169188) to undergo repeat FACBC study to determine if abnormality persists. Yet, since the PPV of FACBC has already proven to be high for extraprostatic disease and FACBC detection in itself is the primary endpoint, this potential limitation would only affect secondary analyses.

FACBC findings will be used for research purposes within the context of the clinical trial as noted above. All incidental findings will be recorded in the clinical research form and emergent incidental findings will be communicated to the patient's physician who is also the principal investigator on this study.

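### Section 7 re-opens ground truth only for FACBC-positive, dissection-negative patients, so composite-reference sensitivity and NPV would be too high, and a repeat FACBC scan could become its own reference

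*Combined protocol and SAP*

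**What the plan says.** Section 7 (Incidental Findings) names one error in the reference standard: "nodes may be missed that are FACBC positive even with nodal dissection leading to an overestimation of false positivity of FACBC". It offers two ways to resolve it. The first is discretionary: "If this is suspected, patients may be followed with conventional imaging as per routine to clarify the ground truth in specific situations". The second is enrolment in a separate trial for PSA failure after prostatectomy, "to undergo repeat FACBC study to determine if abnormality persists". It adds that "this potential limitation would only affect secondary analyses".

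Section 9 says of extended pelvic nodal dissection: "Note that the latter is not regarded as a gold standard for extraprostatic disease detection since it may still results in substantial false negatives". That statement is not limited to FACBC-positive patients. Section 9 estimates sensitivity as "the percent of positive FACBC among patients with extraprostatic disease detected by extended pelvic nodal dissection" and measures agreement with dissection by kappa.

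Section 3 (Primary Aim, part 2) uses a wider reference for diagnostic performance: histology and/or correlative imaging. No section says whether Section 7 follow-up feeds that composite.

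Section 4 (Tissue and Data Management) covers everyone: "Patients will also be followed for long term outcome measures correlating FACBC findings with PSA and clinical recurrence". It plans consent for ten years of record-based follow-up but places that endpoint outside this trial.

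**The concern.** A patient re-opened under Section 7 either stays a false positive or becomes a true positive. The matching check in FACBC-negative patients, which could turn a true negative into a false negative, is not provided. Dissection misses are therefore corrected where they count against FACBC and left alone where they count for it.

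The repeat-scan route has two further weaknesses. It lets the index test contribute to its own reference, and benign uptake can persist as well as malignant uptake. It is also reached through later PSA failure, with no time limit, whereas the hypothesis concerns disease present at diagnosis.

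At stake is the second part of the Primary Aim, which the plan treats as a secondary analysis.

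**Working it through.** **Inputs from Section 9:** N = 88, prevalence 50%, sensitivity 40%, specificity 95%.

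**The plan's own figures reproduce.** Positive rate = 0.5 × 0.40 + 0.5 × 0.05 = 0.225. PPV = 0.20 / 0.225 = 88.9%. Expected positives = 88 × 0.225 = 19.8. The binomial 2.5% and 97.5% points are 12 and 28. All match Section 9.

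**True 2×2 table.** With 44 diseased and 44 not: TP 17.6, FN 26.4, FP 2.2, TN 41.8. True NPV = 41.8 / 68.2 = 61.3%.

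**Assumption.** The documents give no detection rate for dissection. Let r be the share of diseased patients that dissection detects, the same whatever the FACBC result, and take r from 0.6 to 0.9.

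**Dissection only.** The cells are TP = 17.6r, FP = 2.2 + 17.6(1 − r), FN = 26.4r and TN = 41.8 + 26.4(1 − r). At r = 0.7 these are 12.3, 7.5, 18.5 and 49.7. So:
- sensitivity 12.32 / 30.80 = 40.0%
- specificity 49.72 / 57.20 = 86.9%
- PPV 12.32 / 19.80 = 62.2%
- NPV 49.72 / 68.20 = 72.9%

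**One-sided, error-free revision.** The 17.6 × 0.3 = 5.3 missed FACBC-positive patients move from FP to TP. The 26.4 × 0.3 = 7.9 missed FACBC-negative patients stay as true negatives. Sensitivity becomes 17.6 / (17.6 + 26.4r).

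| r | Sensitivity | Specificity | PPV | NPV |
|---|---|---|---|---|
| 0.9 | 42.6% | 95.3% | 88.9% | 65.2% |
| 0.8 | 45.5% | 95.5% | 88.9% | 69.0% |
| 0.7 | 48.8% | 95.8% | 88.9% | 72.9% |
| 0.6 | 52.6% | 96.0% | 88.9% | 76.8% |
| True value | 40.0% | 95.0% | 88.9% | 61.3% |

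The revision does not itself move NPV. NPV is too high because the FACBC-negative group is never checked. Error-free follow-up of both groups restores the last row exactly.

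**If persistent uptake on repeat FACBC were scored as disease in every open patient (r = 0.7).** The 2.2 real false positives convert too. PPV and specificity become 100%, and sensitivity is 19.8 / (19.8 + 18.48) = 51.7%. This is an upper bound, not a rule in the plan.

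**If FACBC guides dissection.** Assume, for illustration, detection of 90% in FACBC-positive and 70% in FACBC-negative patients. Dissection-only sensitivity is 15.84 / (15.84 + 18.48) = 46.2%, and after revision it is 17.6 / 36.08 = 48.8%. Section 7 then adds 2.6 points rather than 8.8. The end value is the same, because much of the excess is already present in the dissection result.

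**The case against.** **Section 9's estimator is immune.** Its sensitivity counts only dissection-positive patients, so no dissection-negative patient can enter it. A reader might infer that the plan's stated sensitivity is inflated by Section 7. It is not: under equal detection it stays at 40%, and kappa against dissection is likewise untouched. The effect needs the Section 3 composite. This objection stands.

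**Most of the PPV and specificity gain is correction.** A reader might take the rise in PPV from 62% to 89% as bias. Under the plan's inputs 89% is the true value, and specificity overshoots its true 95% by at most one point. This also stands.

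**The 100% scenario is not planned.** Section 7 says a patient could have a repeat scan. It does not say that persistent uptake is scored as metastasis, and entry also requires PSA failure and enrolment. This stands too, but nothing rules such scoring out.

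**Independence is doubtful.** Section 4 lets FACBC findings extend and guide the dissection, so misses may be rarer in FACBC-positive patients. The shift due to Section 7 is then smaller, as shown above.

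**Some FACBC-negative patients are verified.** Section 4 allows sampling prompted by conventional imaging. That occurs around surgery and gives no counterpart to the later re-opening.

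**Only secondary analyses are touched.** Section 7 says so and is right; the primary endpoint is the FACBC positivity rate. That limits the importance of the point but does not remove it. Section 7's further reassurance, that PPV is already known to be high, leans on experience that Section 1 describes as mostly post-treatment recurrence.

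**Conclusion.** The point holds in a conditional form. If Section 7 revisions enter the composite reference, sensitivity is overstated (43% to 53% against 40%), NPV is left too high (65% to 77% against 61%) and specificity is slightly high (95.3% to 96.0% against 95%). PPV is unbiased under error-free follow-up. PPV and specificity are inflated further only if persistent uptake on a repeat FACBC scan counts as disease.

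These sizes rest on the plan's own prevalence and accuracy, on an assumed detection range of 60% to 90%, on detection independent of FACBC, and on complete, error-free follow-up of the FACBC-positive group. Section 7's discretionary wording could make the actual shift smaller.

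The documents do not support the broader reading that every accuracy figure is biased in FACBC's favour. Nor do they settle whether the dissection-only or the composite table should be the main one. That is a trade-off: the first carries dissection misses into PPV and specificity, and the second depends on the quality of follow-up.

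**What to change.** In Sections 7 and 9:

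1. State that a repeat FACBC scan is never part of the reference standard for FACBC.
2. State that Section 7 follow-up does not alter the dissection-based cross-table, sensitivity or kappa.
3. Allow follow-up reclassification only in a composite-reference 2×2 table, by one pre-specified rule (non-FACBC imaging, biopsy or PSA taken from the record) and one time window, applied to all dissection-negative patients whatever their FACBC result. Report that table beside the dissection-only one.

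The cost is wording plus review of records for which consent is already planned. No scan is added and no patient's care changes. Composite sensitivity and NPV will look less favourable than under the one-sided rule.
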